At the same time this symptomatology is identified as under-estimated and under-treated. Hubbard et al (2014), in accordance with the guidelines, suggest the need to introduce assessment of fatigue as a screening element for normal clinical practice. Interventions aimed at increasing physical activity, psychosocial and pharmacological support can benefit patients even if a standard treatment model has not been described to date (Bower, 2014). One of the difficulties highlighted in the literature is the correct identification of this syndrome. Scott et al (2011) stress the need for systematic studies in cancer populations with different types of cancer and at different stages of the disease using patient-oriented fatigue assessment tools. The Brief Fatigue Inventory (BFI) is one of the scales used precisely in the evaluation of this syndrome and has proved to be a reliable and easy to use tool, also validated in Italian (Mendoza et al 1999, Catania et al. 2013). Several authors have also shown that reduced physical activity and a worse quality of life are associated with fatigue (Witt et al 2002; Stark et al 2012, Warner et al 2008), particularly in young patients (Poort et al 2017) .

In the area of bone tumors, the available data on fatigue syndrome are extremely poor and only two studies have emerged from the literature search. The study by Granada-Cameron et al (2011) describes the experience of 11 new sarcoma patients undergoing chemotherapy treatment. Fatigue had been described as the prevalent symptom and was related to a worse quality of life.

Serveas et al (2003) observing patients two years after the conclusion of treatment for bone cancer found that in 28% of cases fatigue is a severe problem for patients.

Objective

The aim of the present study is to evaluate and describe the evolution over time of the fatigue and the quality of life of patients with bone tumor during the chemotherapy treatment and in the first phase of follow-up and to identify possible prognostic factors. Such knowledge is a necessary precondition for identifying patients and the periods most at risk due to the onset of fatigue, so as to be able to hypothesize adequate containment strategies.

Setting: Rizzoli Orthopedic Institute. Department of Chemotherapy

Methods

Design: observational study

Population: all patients belonging to the Chemotherapy ward will be recruited consecutively for a new antineoplastic treatment protocol. The process of informing and collecting the participants' consent will take place during the first admission in which intravenous administration of the chemotherapy will be started. Potential participants will be identified / selected for recruitment through inclusion and exclusion criteria described below. Enrolled patients who will not continue the chemotherapy protocol within our Institute but at another facility will exit the study.

Inclusion criteria:

all patients diagnosed with bone tumors who start a new chemotherapy treatment protocol, both on admission and on an outpatient basis at the Chemotherapy ward for its antineoplastic treatment over 12 years of age. The NCCN Guidelines Cancer-Related Fatigue identifies appropriate screening with rating scales with scores from 0 to 10 precisely for patients older than 12 years.

Exclusion criteria:

patients with little knowledge of the Italian language due to the impossibility of completing the assessment scales.

Primary outcome:

the patient's Fatigue will be measured during the treatment period with antineoplastic drugs and part of the followup period. To this end the BFI scale validated in Italian will be used (Mendoza et al 1999; Catania et al, 2013) which includes 9 items with a score for each of 0 to 10 and a consequent total score from 0 to 90. The measurement will take place in 4 times: the day of enrollment, 6 months, 12 months and 24 months after enrollment.

Secondary outcome:

the quality of life of patients measured by the EORTC QLQ C-30 scale (Aaronson et al, 1993) and the level of autonomy measured by the TESS scale (Davis et al, 1996) in 4 steps: the enrollment day , at 6 months, at 12 months and at 24 months from enrollment.

Variables taken into consideration: through the literature search and the comparison between professionals of different disciplines (nurses, physiotherapists, oncologists) involved, a panel of variables was established to collect:

- Age
- sex
- BMI
- Smoking
- diabetes

- cardiopathies (hypertension, previous heart attack, ...)
- Comorbidity (pulmonary, renal, anemia, arthritis, neuromuscular complications, sleep disorders, pain, emotional distress)
- Diagnosis,
- presence of metastases at the entrance
- type of chemotherapeutic protocol / drug that will be administered from the time of enrollment (Methotrexate, Cisplatin, Adriamycin, Ifosfamide, Elastomer Ifosfamide, Gemcitabine, Taxotere, Vincristine-Adriamycin-ifosfamide, Vincristine - phosphamide-Dactomycin, Ifosfamide-etoposide, Temiri, Topotecan, Cyclophosphamide, Eribulin)
- previous chemotherapy treatments: chemotherapy protocol / drugs already performed (Methotrexate, Cisplatin, Adriamycin, Ifosfamide, Elastomer Ifosfamide, Gemcitabine, Taxotere, Vincristine-Adriamycin-ifosfamide, Vincristine - phosphamide-Dactomycin, Ifosfamide-etoposide, Temiri, Topotecan, Cyclophosphamide , Eribulina) and number of cycles already carried out.
- number of therapy cycles carried out from the moment of enrollment (to be collected at the 24th month)
- tumor location
- surgery (date and type)
- Perceived pain measured with the NRS scale in the 4 expected data collection times

Data collection: the data will be collected at the Chemotherapy ward at the time of admission of the patient in the ward or of his access to the outpatient service. Nurses and the research physiotherapist will be responsible for collecting data by administering the assessment scales and consulting the patient's clinical documentation. Data collection times and specific collection methods are shown in the following tables:

1° day			
DIAGNOSIS/new protocol			
Consent/CRF	6 months		
BFI	BFI	12 months	
QLQ	QLQ	BFI	24 months
TESS	TESS	QLQ	BFI
		TESS	QLQ
			TESS

Variables	Collection methods	Responsible for the collection
Age	Health documentation - to be included in the enrollment form, then a calculation sheet	Nurse
Sex	Health documentation - to be included in the enrollment form, then a calculation sheet	Nurse
BMI	To be calculated: report the patient's weight and height at the entrance	Nurse
Smoking	OBSERVATION sheet (CRF): report in a calculation sheet	Nurse
diabetes	OBSERVATION sheet (CRF): report in a calculation sheet	Nurse
cardiopathies	OBSERVATION sheet (CRF): report in a calculation sheet	Nurse
Diagnosis	Enrollment form: to be reported in the calculation sheet	Nurse
presence of	Sanitary documentation: to be included in the	Nurse

metastases at the entrance	OBSERVATION (CRF) form, then calculation sheet	
type of chemotherapeutic protocol	Enrollment form: to be reported in the calculation sheet	Nurse
previous chemotherapy treatments	Health documentation - to be included in the enrollment form, then a calculation sheet	Nurse
number of therapy cycles	OBSERVATION sheet (CRF): to be found in health documentation and then in the calculation sheet)	Nurse
tumor location	Enrollment form: to be reported in the calculation sheet	Nurse
surgery (date and type)	OBSERVATION sheet (CRF): report in a calculation sheet	Nurse
Pain	Measured with NRS scale. Data present in the BFI Sheet: to be reported in the calculation sheet	Nurse
Autonomy level	TESS scale: self-filled by the patient (6-12-24 months from enrollment)	Physiotherapist

Statistical analysis: The characteristics of the sample will be described using the mean and standard or median deviation and interquartile range for quantitative variables and absolute and percentage frequencies for qualitative variables. Simple and multiple linear regression analyzes will be performed and to identify predictors of primary and secondary outcome.

Sample size: In a pilot study of 19 patients at the Chemotherapy SSD the average BFI score was 31.6 with DS 19.1 at a mean follow-up of 5.2 months and DS 3.7. On the basis of this data, the number of variables taken into consideration equal to 15 in a multiple linear regression, an effect size of 0.1, an alpha value of 0.05 and a power of 80% the

number of patients to be enrolled is equal to 183. The sample size was calculated with Stata 15.0.

Duration of the study: The project lasted 5 years as follows:

Month 1-3 Meeting and training of the team involved in the study

Months 3–36 Patient enrollment and data collection.

Months 36-48 Construction of the database and preliminary analysis

Months 48-60 Follow-up and Statistical analysis of data

The approval date of the Ethics Committee will be considered as the starting date of the trial.

Safety assessment: as this is an observational study, patients will be treated in accordance with the rules of good clinical practice and in accordance with the protocols regularly used in the operating unit involved.

Data management and informed consent: the personnel designated by the Investigator must report the information required by the protocol in the CRF form and subsequently in the prepared database. Each potential participant will be fully explained the progress of the study and will be given the opportunity to ask questions and receive answers to all his doubts. The informed consent form must be signed by the participant or a legally authorized representative prior to his participation. Patient documentation must be able to demonstrate that consent was given prior to participation in the study. A copy of the informed consent form must be left to the patient. The consent form, signed by the patient, must be kept at the site.

Approval by the Ethics Committee: This protocol, the informed consent form and all the necessary relevant information related to the study must be submitted to the Ethics Committee for evaluation and must be approved before the start of the study. The study will be conducted in accordance with international standards ISO 14: 155, with the Good Clinical Practice and with the national laws in force.

Confidentiality of data and ownership of results: Adequate documentation will be maintained for everything concerning the patient's clinical data, work sheets, nursing notes; the database will be available in a protected environment and access allowed only with Password. The confidentiality of the patient's sensitive data is guaranteed by the Investigator.

Publication of Results: The main investigator undertakes to produce the final report, publish all the data collected as described in the protocol and ensure that the data is reported responsibly and consistently. In particular, the publication of the data deriving from this study will take place regardless of the results obtained. The transmission or diffusion of the data, through scientific publications and / or presentation at congresses, conferences and seminars, will take place exclusively following the merely statistical elaboration of the same, or in any case in an absolutely anonymous form.

Bibliografya

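### Disease and vital status are not recorded after entry, so a change in mean BFI over 24 months cannot be separated from selective loss or relapse

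*Protocol*

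**What the plan says.** The Objective section of the protocol sets out to "evaluate and describe the evolution over time of the fatigue and the quality of life of patients with bone tumor", through chemotherapy and the first phase of follow-up. It also aims to find prognostic factors and the periods of greatest risk. For the BFI, the Primary outcome section states: "The measurement will take place in 4 times: the day of enrollment, 6 months, 12 months and 24 months after enrollment".

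Under Variables taken into consideration, disease state appears once, as "presence of metastases at the entrance". The same list includes "previous chemotherapy treatments: chemotherapy protocol / drugs already performed", so patients treated before are expected in the cohort.

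The items that can change after entry are surgery (date and type), a single count of cycles taken at month 24, and "Perceived pain measured with the NRS scale in the 4 expected data collection times". The BFI, QLQ-C30 and TESS are also repeated. The table under Data collection adds no further disease item, and it takes the chemotherapy regimen from the enrollment form.

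The one exit rule, under Population, is: "Enrolled patients who will not continue the chemotherapy protocol within our Institute but at another facility will exit the study".

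**The concern.** Comparing means at 0, 6, 12 and 24 months describes the course of fatigue only if the reader knows who is still being measured and in what disease state. In a mixed cohort followed for two years, some patients may relapse, progress or die. Nothing in the panel records these events or says why a scale is missing.

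Two things then cannot be resolved from the study database. An absent month-24 BFI after a death looks like one after a refusal. A high month-24 BFI in a relapsed patient under new treatment looks like late fatigue in a patient who has finished treatment and is well. Both bear on the main description and on which periods are called high-risk.

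This is a matter of what is collected. A statistical analysis plan can choose a method for missing data, but it cannot condition on survival or split by relapse if those events are not in the data.

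**Working it through.** **1. Inventory.** The list of variables and the collection table were checked against the events that matter.

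- Disease state at entry: recorded (metastases).
- Relapse, progression or new metastases after entry: no field.
- Vital status or date of death: no field.
- Reason for a missed scale: no field.
- Transfer to another facility: a defined exit, but with no listed field.
- Surgery, cycle count, pain, QLQ-C30 and TESS: recorded after entry, but none of them identifies relapse or death.

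**2. Inputs.** The Sample size section gives a pilot BFI mean of 31.6 with SD 19.1 (19 patients, mean follow-up 5.2 months) and a target of 183 patients. The target reproduces if the effect size of 0.1 is read as R². Then f² = 0.1/0.9 = 0.111, and with 15 predictors the overall F test (df 15 and N − 16, noncentrality N × f²) reaches power 0.803 at N = 183. Here 183 serves only as the starting number. The fraction lost, p, and the enrolment gap between lost and retained patients, g (in SD units), are not in the protocol and are assumed.

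**3. Formula.** Let m_R and m_L be the enrolment means of the retained and the lost patients. The full-cohort mean is (1 − p) × m_R + p × m_L = m_R + p × (m_L − m_R). If no patient changes, the observed mean therefore moves from enrolment to month 24 by −p × g × 19.1.

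**4. Numbers.** With g = 0.5 the gap is 0.5 × 19.1 = 9.55 points. The last column is 1.96 × 19.1/√n for the n patients left.

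| Lost | n left | Fall, g = 0.5 | Fall, g = 1 | 95% half-width of a mean |
|---|---|---|---|---|
| 10% | 165 | 1.0 | 1.9 | 2.9 |
| 20% | 146 | 1.9 | 3.8 | 3.1 |
| 30% | 128 | 2.9 | 5.7 | 3.3 |
| 40% | 110 | 3.8 | 7.6 | 3.6 |

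At g = 0.5 and 10% to 30% lost, the shift stays below the half-width. It exceeds it only at 40% lost, or at a 1 SD gap with 20% or more lost. The half-width is that of a single mean and is a yardstick only.

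**5. Direction.** If the lost patients were less fatigued than the rest, g is negative and the mean rises by the same amounts. This is possible, because the scales are given on the ward or at outpatient visits, and well patients may stop attending.

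**6. What the planned data can and cannot show.** Enrolment BFI is available for everyone. Comparing it between patients with and without a month-24 score would expose the shift in step 4, and in patients measured both times the change would be zero. Two things stay hidden. The first is worsening after enrolment in patients lost before their next assessment. The second is relapse among patients still assessed: if a fraction r has relapsed and this raises their BFI by h, the mean is r × h higher. The documents give neither r nor h, and r could not be computed from the planned fields.

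**The case against.** The case on the other side has real substance.

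- The shifts of 1.0 to 2.9 points describe selective loss in general. Enrolment BFI alone could reveal them, without a disease or vital status field. This stands, so the figures illustrate scale and do not measure the harm of the omission.
- The SD comes from 19 pilot patients at a mean of 5.2 months and is applied here to enrolment scores. This stands as a limit on the figures.
- A reader might infer that a falling mean BFI would be an artefact of losing the sickest patients and would be taken for recovery. The documents do not support that. They give no loss or death rate, and the place of data collection makes loss of well patients possible too.
- A reader might also infer that relapse undermines the search for prognostic factors. It does not: an entry characteristic that predicts late fatigue by way of relapse is still a valid prognostic factor, and the protocol makes no causal claim. Metastases at entry and earlier chemotherapy are recorded, so higher-risk patients can be separated.
- Transfer is a defined exit, so it should not be treated as simply indistinguishable from death. The CRF is not shown, although the collection table lists what is to be collected.
- The events may be recoverable later from hospital records. That is partly true, but deaths and relapses managed elsewhere may be missed, and nothing in the protocol asks for the abstraction.
- How the BFI course is conditioned and displayed could sit in a statistical analysis plan. What is collected is fixed in this protocol.

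What remains is the gap in collection itself, which none of these points closes.

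**Conclusion.** The point holds in a limited form. Followed as written, the study cannot separate a real change in fatigue from a change in who is measured or in their disease state, and this weakens its own aim of describing fatigue over time and finding the periods of risk.

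The size is unknown. The illustrative 1.0 to 2.9 points rest on three assumptions: 10% to 30% lost, a 0.5 SD gap at enrolment, and the pilot SD of 19.1. With up to 40% lost and a gap of up to 1 SD, the shift reaches 7.6 points. Either sign is possible. The study is not invalid without the change, but the change is inexpensive and makes its central description interpretable.

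**What to change.** Add three items to the list of variables, the collection table and the CRF, taken from health documentation at 6, 12 and 24 months:

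- disease status since the last assessment (no evidence of disease, stable, or relapse or progression), with the date of relapse or progression;
- vital status, with date of death;
- the reason for each missing scale (for example death, too ill, transfer, no longer attending, refusal).

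Describe the BFI course as that of patients alive and assessed at each time. Show it beside the course in patients with all four assessments, and by relapse or progression status. If enrolment has begun, abstract the same items retrospectively and note where events outside the institute may be missed.

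The nurses already consult these records, so no visit or patient burden is added and no treatment changes. The cost is minor data-entry work and one extra descriptive table.

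### Cycles since enrolment are recorded only as one month-24 total, so a regression of 6- or 12-month BFI on it can count cycles given after the score

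*Protocol*

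**What the plan says.** All references are to the protocol.

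- **Variables taken into consideration.** The panel includes the "number of therapy cycles carried out from the moment of enrollment (to be collected at the 24th month"). The neighbouring items are handled differently: surgery is recorded with its date, and pain is "Perceived pain measured with the NRS scale in the 4 expected data collection times".
- **Data collection table.** The row for cycles gives only a source, "to be found in health documentation and then in the calculation sheet", with no count or date at 6 or 12 months.
- **Primary outcome.** "Fatigue will be measured during the treatment period with antineoplastic drugs and part of the followup period". "The measurement will take place in 4 times: the day of enrollment, 6 months, 12 months and 24 months after enrollment".
- **Statistical analysis.** "Simple and multiple linear regression analyzes will be performed and to identify predictors of primary and secondary outcome". No regressors are listed and no outcome visit is named.
- **Sample size.** The calculation uses "the number of variables taken into consideration equal to 15 in a multiple linear regression".
- **Autonomy level row of the data collection table.** "TESS scale: self-filled by the patient (6-12-24 months from enrollment"). The Secondary outcome section and the visit diagram both place TESS on the enrolment day as well.

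**The concern.** The Objective asks for prognostic factors that would help to identify patients, and periods, at risk of developing fatigue. A count that becomes known only at month 24 cannot flag a patient in advance. For the 6- and 12-month scores it can also look ahead. If fatigued patients later receive fewer cycles, or more, the total carries that information back into a model of the earlier score. A backward association could then be reported as a predictor.

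This is a data-collection matter as well as a modelling one. A later analysis plan can choose the visit and the model, but it cannot divide a single stored total into counts to month 6 and month 12 without returning to the charts.

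A related and lesser point is that the enrolment BFI score is collected but appears in neither list of variables. Without it, factors for new fatigue cannot be separated from factors tied to fatigue already present. The protocol's own bibliography includes a study whose title links chemotherapy-induced fatigue to higher scores before treatment.

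**Working it through.** **1. Is the total a planned regressor?** The panel has 15 entries: age, sex, BMI, smoking, diabetes, cardiopathies, comorbidity, diagnosis, metastases, chemotherapy type, previous chemotherapy, cycles, tumour location, surgery, pain. The collection table also has 15 rows, but drops comorbidity and adds autonomy level. Both contain the cycle total and neither contains enrolment BFI. The sample size uses 15 variables and echoes the heading of the panel. That the panel is the regressor set is therefore a reasonable inference, but the protocol does not state it.

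**2. Reproducing N = 183.** Overall F test, k regressors, noncentrality λ = N·f², f² = R²/(1 - R²), degrees of freedom k and N - k - 1. From the protocol: k = 15, alpha 0.05, power 80%, effect size 0.1. Read as R² = 0.1, f² = 0.1/0.9 = 0.111. Then λ = 183 × 0.111 = 20.3 on 15 and 167 degrees of freedom, and power is 80.3%. N = 183 is the smallest N that reaches 80%.

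| Variables | N for 80% | Power at N = 183 |
|---|---|---|
| 14 | 178 | 81.7% |
| 15 | 183 | 80.3% |
| 16 | 187 | 78.8% |

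**3. Look-ahead for a 6- or 12-month model.** Everything in this step is assumed except n = 183, 15 regressors and the pilot SD of 19.1. Write the standardised total as √(1 - s)·earlier + √s·later, where s is the share of its variance due to cycles after the visit. Let earlier cycles have no effect on BFI and let r be the correlation of later cycles with that visit's BFI. The total then correlates √s·r with BFI, and its coefficient is 19.1·√s·r BFI points per SD of cycles. At s = 0.25 and r = -0.3 this is 19.1 × 0.5 × (-0.3) = -2.9 points.

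Share of studies in which the total is significant at two-sided 5% (simulation, 10,000 studies per cell):

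| s | r = -0.1 | r = -0.2 | r = -0.3 | Coefficient, points per SD |
|---|---|---|---|---|
| 0.25 | 10.0% | 25.4% | 49.9% | -1.0 to -2.9 |
| 0.10 | 6.9% | 13.3% | 22.8% | -0.6 to -1.8 |
| 0.05 | 5.9% | 8.5% | 14.0% | -0.4 to -1.3 |
| 0 | 4.8% | 4.9% | 4.9% | 0 |

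A noncentral F calculation agrees: 9.9/25.4/49.8%, 6.9/12.9/23.3% and 6.0/8.9/13.9% for the first three rows. Counting earlier cycles only gives 4.6 to 5.4%.

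**4. A real effect of earlier cycles is distorted too.** Assume cycle counts before and after month 6 each have mean and variance 6, and early cycles correlate 0.3 with 6-month BFI. The slope per early cycle is 0.3 × 19.1/√6 = 2.34 points. If later cycles are unrelated to the score, the slope on the total is 0.3 × 19.1 × √6/12 = 1.17. By simulation it is -0.96 if later cycles correlate -0.5 with the score and +2.88 if they correlate +0.5.

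**5. Effect on the other coefficients.** Take an enrolment factor with standardised effect 0.2 or 0.3, s = 0.10 or 0.25, r = -0.1 or -0.3. If it is unrelated to earlier cycles, its coefficient shifts by at most about 2%. If it correlates 0.3 to 0.5 with them, the shift is about 3 to 36%. The 36% is the extreme corner (effect 0.2, s = 0.25, r = -0.3, correlation 0.5): 0.36 × 0.2 × 19.1 = 1.4 BFI points on a 0 to 90 scale.

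**6. Enrolment score as covariate.** If it correlates ρ = 0.3 to 0.6 with the visit score (assumed), residual variance falls by ρ² = 9 to 36%. This takes the score alone; with the other regressors in the model the partial correlation governs, and the gain may differ.

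**The case against.** The strongest reply is that harm depends on choices the protocol has not made: a 6- or 12-month outcome, use of the month-24 total in that model, and a material share of cycles after that visit. The document gives neither treatment length nor cycle numbers. This stands. It makes the point conditional and its size unknown, and the grid above includes the null case.

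Second, the count comes from clinical documentation that staff consult anyway, so counts to each visit can probably be recovered. This also stands, and a reader who inferred that the information is lost for good would go too far. It is nevertheless cheaper to count by visit during collection than to reopen every chart, and the protocol as written does not plan it.

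Third, the absence of enrolment BFI from the lists does not bar it from a model. The panel lists variables to collect beside the outcomes, and covariate choice is commonly left to an analysis plan. Adjustment also changes the question: a factor that acts through fatigue already present at enrolment loses part of its effect. This stands. One might infer that leaving the score out is a mistake, but predictors of fatigue level are a valid target too, and the documents do not support calling it one.

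Fourth, restricting prognostic models to enrolment variables would be broader than the defect requires, since pain is deliberately recorded at all four times. That is right. The need is only that cycles and surgery in a model do not post-date the score.

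**Conclusion.** The point holds in conditional form and should be fixed. A total collected only at month 24 suits a month-24 model as an explanatory correlate, though it is not known in advance. It does not suit a 6- or 12-month model, where it can turn later treatment into an apparent predictor of earlier fatigue. Depending on assumptions that the documents cannot settle, the false-positive rate for the cycle coefficient runs from 5% (no later cycles) to about 50%.

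Two stronger readings are not supported. One is that the sample size is wrong: 183 reproduces exactly at R² = 0.1 with 15 variables, and the timing of the count does not enter it. The other is that the whole analysis is compromised: the description of fatigue over time is unaffected, and coefficients of enrolment factors unrelated to earlier cycles hardly move. That the 15 regressors are the 15 panel items remains an inference.

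The TESS timing is a plain inconsistency within the protocol. If the table row is followed, there may be no baseline TESS score.

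**What to change.** 1. **Variables taken into consideration.** Replace the month-24 total by: *number of cycles since enrolment, counted up to each visit from the clinical records, with the date of the last count for patients who exit the study*. State that any model uses only cycles, and dated surgery, up to the visit modelled.
2. **Statistical analysis.** Include the enrolment score of the modelled scale (BFI, QLQ-C30 or TESS) as a covariate in the 6-, 12- and 24-month prognostic models. Report the models without it as well if predictors of fatigue level are of interest. This is an improvement, not the correction of an error.
3. **Data collection table.** Reconcile the TESS row with the Secondary outcome section and the visit diagram, so that a baseline score exists.

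**Cost.** A little more extraction from charts already consulted, and three short edits. At R² = 0.1 and N = 183, exchanging cycles for enrolment BFI keeps 15 variables and 80.3% power. Moving surgery out as well leaves 14 and 81.7%. Adding enrolment BFI while keeping cycles makes 16 and 78.8%, or N = 187 for 80%. The last figure is conservative, because enrolment BFI would be expected to raise R². If R² rose to 0.19 (assumed), f² = 0.19/0.81 = 0.235 and power at 183 would be about 99%.

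### The listed variables do not show whether a patient is on or off chemotherapy at the 6-, 12- and 24-month BFI assessments, so changes in fatigue cannot be told apart from changes in treatment mix

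*Protocol*

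**What the plan says.** The Objective section of the protocol sets the time window as "during the chemotherapy treatment and in the first phase of follow-up". It presents the resulting knowledge as a precondition for "identifying patients and the periods most at risk due to the onset of fatigue". The Primary outcome section names the same two phases: fatigue "will be measured during the treatment period with antineoplastic drugs and part of the followup period".

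The schedule runs on calendar time: "The measurement will take place in 4 times: the day of enrollment, 6 months, 12 months and 24 months after enrollment". Under Population, enrollment takes place at the first admission at which intravenous chemotherapy begins. Under Data collection, the scales are given "at the time of admission of the patient in the ward or of his access to the outpatient service", with no rule on where this falls within a chemotherapy cycle.

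Any patient over 12 years with a bone tumor who starts a new protocol may enter. The list under Variables taken into consideration names 14 drugs or combinations and allows for earlier chemotherapy. For treatment after enrollment it gives the type of protocol or drug, surgery with date and type, and one total: "number of therapy cycles carried out from the moment of enrollment (to be collected at the 24th month"). Pain, by contrast, is expressly collected at all four times.

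**The concern.** Both the aim and the primary outcome refer to treatment phase, but months since enrollment are only a rough stand-in for it. Patients on different regimens, with different treatment histories, need not finish chemotherapy at the same time. The mean BFI at 6 or 12 months may therefore combine patients still on treatment with patients who have finished.

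Two things are at stake. First, a rise or fall in mean BFI between visits could come partly or wholly from a change in the share of patients on treatment, and the listed data give no means of checking this. That weakens any statement about which periods carry the most risk. Second, the only cycle count since enrollment is taken at the end. Used as a predictor of BFI at month 6 or 12, it would contain exposure that came after the outcome.

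An analysis plan cannot repair this later if the information is never recorded.

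**Working it through.** **1. What the listed variables say about phase at each assessment.**

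- Day 0: phase is known, because enrollment coincides with the start of intravenous chemotherapy.
- Months 6, 12 and 24, regimen type: says what was started, not whether it is still being given.
- Months 6, 12 and 24, surgery: carries a date, but not a chemotherapy date.
- Months 6, 12 and 24, cycle total: undated and cumulative to month 24. A patient who finished before month 6 and a patient still on treatment at month 12 can have the same total.
- Neither the variable list nor the collection table contains on/off status, a last-administration date, an end-of-chemotherapy date or a cycle count at 6 or 12 months.

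Phase at the three later assessments therefore cannot be recovered from the listed items.

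**2. Order in time of the cycle count.** The month-24 total equals cycles up to month 6, plus cycles from month 6 to 12, plus cycles from month 12 to 24. For BFI at month 6 the last two parts come after the outcome; for BFI at month 12 the last part does. The total is therefore not a valid predictor of either score.

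**3. Possible size of the mix effect.** The protocol gives no treatment durations and no on/off difference in BFI, so both are assumptions. Let d be the on/off difference in mean BFI, and p1 and p2 the shares on treatment at two visits. If mean fatigue within each state does not change, then

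change in overall mean = d × (p2 − p1).

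With d of 5 to 10 points and a fall in share of 0.30 to 0.60, the size of the shift is:

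- 5 × 0.30 = 1.5 points
- 5 × 0.60 = 3.0 points
- 10 × 0.30 = 3.0 points
- 10 × 0.60 = 6.0 points

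Against the pilot SD of 19.1 (Sample size section) this is 1.5/19.1 = 0.08 to 6.0/19.1 = 0.31 SD, with no change in fatigue within either state.

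**4. The planned sample size is not affected.** The stated 183 reproduces. With 15 predictors, alpha 0.05, power 80% and the effect size of 0.1 read as R², f² = 0.1/0.9 = 0.111. The overall F test with noncentrality N × f² then gives N = 183 (power 80.3%). Replacing the month-24 total with cycles to date keeps 15 predictors. On the same reading, adding one predictor would need 187 patients and adding two would need 192.

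**The case against.** The strongest reply is that the aim is to describe the course of fatigue over time and to find prognostic factors. No contrast between on-treatment and off-treatment fatigue is stated. Time since the start of a new protocol is a legitimate time origin, the periods at risk can be read as the four calendar times, and a changing treatment mix is then part of the natural course. This stands in part: the calendar-time description is valid and should be kept. It does not remove the point, because the Objective and Primary outcome sections themselves name treatment and follow-up, and a reader of the results will want to know which of the two a 6- or 12-month mean represents.

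A reader might infer that the study can never separate the two phases. The documents do not support that. Phase is known at day 0, staff consult the clinical documentation, and patients who continue the protocol at another facility leave the study, so treatment dates are probably retrievable. The CRF is also not shown. However, the Data management section ties the CRF to what the protocol requires, and the protocol does not require these items.

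A reader might also call the cycle count the only exposure variable after enrollment. Regimen type and surgery are listed too; what is missing is dating.

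Finally, on/off status is a post-baseline state partly determined by regimen, so adjusting for it can remove part of the regimen effect that a prognostic analysis seeks. That objection is sound and limits the remedy.

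**Conclusion.** The point holds for the 6-, 12- and 24-month assessments and for the data the protocol lists. Those data do not identify treatment phase, so they cannot show whether a change in mean BFI between visits is a change in fatigue or in the share of patients on treatment. The month-24 cycle total is not a valid predictor of the 6- and 12-month scores; this follows from timing alone.

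The 1.5-6 point range rests entirely on the assumed on/off difference and fall in share. The gap in the variable list does not depend on it. It would be tempting to turn the same assumptions into a share of BFI variance and set that against the planned effect size of 0.1. That comparison should not be made: 0.1 is an input to the power calculation, not a ceiling on explained variance, and the pilot SD may already contain on/off mixing.

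The study remains feasible and its sample size is untouched. This should be corrected, but it does not show that the objective has failed.

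**What to change.** At the 6-, 12- and 24-month assessments, record from the clinical documentation:

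- on or off chemotherapy
- current regimen
- cycles given so far since enrollment
- date of last administration

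Record the end-of-chemotherapy date once. Where assessments have already taken place, the same items can probably be filled in from the records.

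Report BFI at each visit overall and by on/off status, with the number of patients in each state. When modelling BFI at a given assessment, use cycles given up to that assessment in place of the month-24 total. Keep any adjustment for on/off status or days since last administration as a supplementary analysis, because these are post-baseline and partly determined by regimen.

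The cost is a few extra CRF fields per visit, read by nurses from records they already consult, with no added visit or procedure. The by-status description will rest on smaller groups: an even split of 183 gives about 91 or 92 per group before any loss to follow-up.
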